#### Concomitant Medications

Concomitant medications will be coded using the WHO Drug Dictionary, version March, 2011 or higher, and will be presented in data listings.

#### Application Site Reactions

Frequency and distribution of application site reactions of erythema, dryness, burning/stinging, erosion, edema, pain and itching will be summarized and compared descriptively by visit.

Safety comparisons will be performed only for the ITT population.

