5.10 Application Site Reaction Assessment

At baseline and each subsequent visit, application site reactions such as erythema, dryness, burning/stinging, erosion, edema, pain and itching are to be recorded. Pain and itching symptoms will be assessed by discussion with the subject and will be reported as the severity experienced within 24 hours of the trial visit.

The Application Site Reaction Assessment must be conducted by qualified investigators listed on the Form FDA 1572 who have been delegated these tasks by the PI. [REDACTED]

[REDACTED]

[REDACTED]

Application site reactions are not to be recorded as adverse events unless they result in either:

- The temporary discontinuation of the study medication.
- The discontinuation of the subject from the study.
- The use of a new concomitant medication in order to treat this event.

Site Reaction	DESCRIPTION
Erythema	[REDACTED]
Dryness	[REDACTED]
Burning/Stinging	[REDACTED]
Erosion	[REDACTED]
Edema	[REDACTED]
Pain	[REDACTED]
Itching	[REDACTED]

SCORE	ASSESSMENT	DESCRIPTION
0	None	Absent
1	Mild	Slight, barely perceptible
2	Moderate	Distinct presence
3	Severe	Marked, intense

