5.11 Study Medication Use, Subject Instructions and Diary

At the baseline visit, one [REDACTED] pump bottle of study medication from the subject kit box will be dispensed to enrolled subjects along with a diary card. Each subject will also receive a copy of written instructions, which detail the proper application method, and general instructions regarding the study (see Appendix B). The initial application on Day 1 will be demonstrated and observed by study staff when the subject applies the medication at the study site to ensure subjects understand the instructions. Subsequent applications of study medication should be applied as demonstrated starting Day 2. [REDACTED]

[REDACTED]. At all subsequent study visits the study medication will be collected to assess study medication accountability. After the compliance evaluation, empty pump bottles will be collected and kept by the site. [REDACTED]

[REDACTED] subject will receive a new pump bottle each at Visit 2/Week 4/Day 28 (± 4 days) and Visit 3/Week 8/Day 56 (± 4 days). However all subjects MUST switch to at least the second new pump bottle by Visit 2/Week 4/Day 28 (± 4 days) or Visit 3/Week 8/Day 56 (± 4 days). The sites must collect pump 1 from each subject by Visit 3/Week 8/Day 56 (± 4 days) . [REDACTED]

A non-medicated, mild cleanser and a facial lotion with sunscreen will be dispensed to the subjects at the baseline visit. Subjects will cleanse their face with the study provided non-medicated, mild cleanser [REDACTED].

[REDACTED]. [REDACTED] the study medication should be applied to the affected areas of the face [REDACTED] and avoiding contact with the eyes, lips, mouth, inside and on angles of the nose, and mucous membranes at approximately the same time once daily for 12 weeks. Subjects will be instructed to wash hands immediately after applying the study medication. Subjects will be instructed to not use any other topical treatments or products other than the study provided facial lotion with sunscreen.

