8.1.5 Safety and Adverse Events Analysis

The frequency and percent of subjects with adverse events will be summarized by MedDRA system organ class and preferred term and by severity and relationship to study drug for all three treatment groups. The adverse events reported by at least five percent of the subjects in any treatment group will also be tabulated. The comparable safety of the Test and Reference

[REDACTED]

treatments will be evaluated by statistical comparison of the proportion of subjects who reported any adverse events. The test and reference treatments' frequency and distribution of application site reactions of erythema, burning/stinging, erosion, edema, pain and itching will be summarized and compared descriptively. Safety comparisons will be performed only for the safety intent-to-treat population.

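### Application site reactions are tabulated by visit only, so the SAP gives no per-subject count of reactions that are new or worse than on Day 1

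*SAP*

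**What the plan says.** **Collection.** Protocol 5.10 states: "At baseline and each subsequent visit, application site reactions such as erythema, dryness, burning/stinging, erosion, edema, pain and itching are to be recorded". Each item is graded 0 (none) to 3 (severe). The grade measures presence and intensity (grade 1 is "Slight, barely perceptible") and carries no attribution to the product. Under the same section, a reaction becomes an adverse event only if it leads to a pause in treatment, withdrawal from the study or a new concomitant medication.

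**Analysis.** The Application Site Reactions paragraph of SAP 5.6 begins "Frequency and distribution of application site reactions of erythema, dryness, burning/stinging, erosion, edema" and ends "pain and itching will be summarized and compared descriptively by visit". It applies to the ITT population and shows no redaction. Protocol 8.1.5 plans the same kind of comparison for the two active products: "The test and reference treatments' frequency and distribution of application site reactions" are to be set side by side descriptively. Its list omits dryness, which the synopsis and the SAP include.

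**What is absent.** The visible text of both documents defines no change from Day 1, no worst post-baseline score, no new-or-worsened rule and no shift table for these scores. For adverse events, by contrast, SAP 5.6 restricts the tables to events on or after the first dose and counts each subject once per preferred term.

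**The concern.** Comparing the safety profiles of Test and Reference is a stated objective (Protocol 2, SAP 2), and Protocol 7 names cutaneous irritation as the reaction related to the reference product. For irritation that triggers none of the three consequences in Protocol 5.10, the by-visit table is the only planned comparison.

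Entry requires an IGA of 3 or 4 (Protocol 5.7), so some facial signs, erythema above all, may plausibly be present on Day 1. A sign that was there on Day 1 and has not changed then counts at Week 4 exactly as a new reaction does. Signs that clear and signs that appear also cancel within a group total. The table therefore cannot answer the question a tolerability reader asks: how many subjects got worse on each product?

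**Working it through.** The documents give no reaction rate, margin or test for these scores, so there is no planned figure to reproduce. The first step is logical. The others illustrate with assumed inputs.

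**1. What by-visit totals leave open.** Suppose a group has a sign in 40% of subjects on Day 1 and in 40% at Week 4. That fits no change in anyone (0% new). It also fits complete clearing plus a new sign in 40% drawn from the 60% who were free of it. If a sign is new in 10% of subjects at each of Weeks 4, 8 and 12, the number of different subjects affected lies anywhere from 10% (the same people) to 3 × 10% = 30% (different people).

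**2. Effect of Day 1 background.** Assumed inputs:
- b = share of subjects with the sign on Day 1
- s = share of those in whom it persists
- p = risk of the sign in everyone not carrying it: 10% Reference, 20% Test
- n = 400 per active arm
- no worsening among those who start with the sign

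Formulas:
- By-visit frequency = bs + (1 − bs)p
- Above own Day 1 score = (1 − b)p
- z = difference / √{[p₁(1 − p₁) + p₂(1 − p₂)]/n}

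Example, b = 40%, s = 1:
- By visit: 0.40 + 0.60 × 0.10 = 46% and 0.40 + 0.60 × 0.20 = 52%.
- Own baseline: 0.60 × 0.10 = 6% and 0.60 × 0.20 = 12%.

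| b | s | By visit, Ref v Test | Diff. (points) | Ratio | z | Above own Day 1, Ref v Test | Diff. (points) | Ratio | z |
|---|---|---|---|---|---|---|---|---|---|
| 0% | – | 10% v 20% | 10 | 2.00 | 4.0 | 10% v 20% | 10 | 2.00 | 4.0 |
| 20% | 1 | 28% v 36% | 8 | 1.29 | 2.4 | 8% v 16% | 8 | 2.00 | 3.5 |
| 40% | 1 | 46% v 52% | 6 | 1.13 | 1.7 | 6% v 12% | 6 | 2.00 | 3.0 |
| 40% | 0.5 | 28% v 36% | 8 | 1.29 | 2.4 | 6% v 12% | 6 | 2.00 | 3.0 |

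For b from 10% to 50% and s of 0.5 or 1, the by-visit ratio runs from 1.66 (b = 10%, s = 0.5) down to 1.09 (b = 50%, s = 1).

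The absolute differences are (1 − bs) × 10 points by visit and (1 − b) × 10 points against own baseline. Since s is at most 1, the by-visit difference is never the smaller one in this model. That depends on the last assumption. If subjects with a Day 1 sign worsened by a grade at the same risk p, the own-baseline measure would show 10% v 20% (10 points), against 6 points for presence at b = 40%, s = 1.

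**3. Scoring noise.** An any-visit rule collects chance upward moves. Assume a 5% chance of one per visit, independent over three visits, so 1 − 0.95³ = 14.3% overall. With b = 40%, s = 1:
- Own baseline, any visit: 1 − 0.94 × 0.857 = 19.4% and 1 − 0.88 × 0.857 = 24.6%; ratio 1.27, z about 1.8.
- By visit, single visit: 1 − 0.54 × 0.95 = 48.7% and 1 − 0.48 × 0.95 = 54.4%; z about 1.6.

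Most of the gain from z = 1.7 to z = 3.0 disappears.

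**The case against.** The case for leaving the plan alone has several parts.

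- **Day 1 may already be shown.** Baseline is Visit 1 and is scored, so a by-visit table can naturally include a Day 1 column. A distribution over grades 0 to 3 would also show a group moving from mild to severe. A reader might infer that the SAP ignores baseline altogether; the text does not support that. What stands is that a column of group totals cannot show change within subjects.
- **Consequential reactions are covered.** Those that lead to a pause, a withdrawal or a new medication become adverse events. They then get the first-dose rule, once-per-subject counting and a statistical evaluation of dermatological events between Test and Reference. The gap concerns the remaining, milder reactions.
- **No inference depends on it.** The comparison is descriptive, with no alpha, margin or success criterion. The z values above only measure contrast.
- **The inputs are assumed.** Arm size, Day 1 prevalence, persistence and reaction risk are not in the visible text. Persistence of 100% is an extreme case when treatment is expected to improve the acne. A Day 1 background is also more plausible for erythema than for erosion or edema, and Protocol 4.2 excludes other facial skin conditions that could interfere with assessment.
- **Timing on Day 1 is not visible.** "The initial application on Day 1 will be demonstrated and observed by study staff", and the order of the visit procedures is blacked out. That the Day 1 score precedes the first dose rests on the word baseline.

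All five objections stand as limits on size and wording. None supplies a per-subject count.

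**Conclusion.** The point holds as a minor one. The planned display omits the number of subjects with a new or worse reaction, although the score needed to derive it is collected. That gap exists whatever the Day 1 prevalence. Day 1 signs also lower the Test/Reference ratio and may reduce precision. How much depends on prevalence, persistence and scoring noise, none of which the documents give, and this dilution is nil if Day 1 scores are near zero.

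A reader might go further and infer that the plan hides a more irritating Test product or biases the comparison. The documents do not support that. Randomisation balances Day 1 signs in expectation, so neither product is favoured in direction. In the table above, the absolute difference is the same under both measures (8 and 8, or 6 and 6 points) or larger by visit (8 against 6). A large gain in sensitivity should not be claimed either: with modest scoring noise it shrinks to about 1.6 against 1.8.

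**What to change.** In SAP 5.6, for the ITT population, for each of the seven reactions and by treatment group, add:

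1. the number and percent of subjects whose worst post-baseline score exceeds their own Day 1 score, with the denominator stated (subjects with a Day 1 score and at least one later score);
2. a shift table of Day 1 score by worst post-baseline score.

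Keep the by-visit table next to these and say that it includes a Day 1 column. The comparison stays descriptive.

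The cost is SAP wording, one derived variable per reaction and one extra table layout. No new data are needed, and the change should be made before unblinding.

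There are two downsides. The any-visit rule accumulates chance one-grade rises, which the shift table lets readers see by grade. The rule also misses a Day 1 sign that fails to resolve, or that clears and returns at the same grade; the by-visit table still shows these.

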## 6 Appendices

### 6.1 Handling of Missing or Incomplete Dates for Adverse Events and Concomitant Medications

#### Adverse Events

Handling of partial dates is only considered for the start date. An adverse event with a partial start date is considered treatment emergent if:

- only the day is missing and the start month/year is the same or after the month/year of the first dose
- the day and month are missing and the start year is the same or greater than the year of the first dose date
- the start date is completely missing

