7.3 Eliciting and Reporting of Adverse Events

The investigator will periodically assess subjects for the occurrence of adverse events. In order to avoid bias in eliciting adverse events, the subject or parent/legally authorized representative should be asked a non-specific question (e.g., "How have you been feeling since your last visit?") to assess whether any AE has been experienced since the last visit. All adverse events (as defined in Section 7.2), either observed by the Investigator or one of his/her medical collaborators, or reported by the participant spontaneously, or in response to direct questioning, will be reported and documented in the source and the study reporting forms. When reporting an adverse event, the Investigator must assign a severity grade to each event and declare an opinion on the relatedness of the event to the study medication or procedure. Serious or unexpected adverse events must be reported to Perrigo **within 24 hours** of when the Investigator first learns of the occurrence of the event.

Adverse events will be documented in source and recorded in a timely manner on case report forms. Adverse events that are identified at the last assessment visit (or the early termination visit) must be recorded on the AE case report form (CRF) with the status of the AE noted.

Adverse event reporting begins from the signing of informed consent/assent. Adverse events should be followed until resolved or 30 days after the final study treatment. In any case, serious adverse events that are not resolved or considered to be chronic within 30 days of the final study treatment must be followed by the investigator until they become resolved or are considered to be chronic (stabilized for at least 30 days). All events that are ongoing at this time will be recorded as ongoing on the CRF.

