9. CONSENT/ASSENT CONSIDERATIONS AND PROCEDURES

It will be made clear to the subject that, for the purposes of the study, they are consenting only for topical application of medication or vehicle. Investigators may discuss the availability of the study and the possibility for entry with a potential subject without first obtaining consent/assent. However, informed consent/assent must be obtained and documented prior to initiation of any procedures that are performed solely for the purpose of determining eligibility for research, including withdrawal from current medication(s). When this is done in anticipation of, or in preparation for, the research, it is considered to be part of the research.

The study must be approved in writing by an appropriate IRB as defined by FDA regulations. A copy of the Letter of Approval from the IRB, which also contains specific identification of the documents approved, must be received by Perrigo Pharmaceuticals, prior to study commencement.

Periodic status reports must be submitted to the IRB at least annually as required by the site's IRB, as well as notification of completion of the study and a final report within three months of study completion or termination. A copy of all reports submitted to the IRB must be sent to Perrigo Pharmaceuticals.

The investigator(s) has both ethical and legal responsibility to ensure that each subject being considered for inclusion in this study is given a full explanation of the protocol. This shall be documented on a written informed consent/assent form, which shall be approved by the same Institutional Review Board (IRB) responsible for approval of this protocol. Each informed consent/assent form shall include the elements required by FDA regulations in 21 CFR Part 50. The investigator agrees to obtain approval from Perrigo Pharmaceuticals of any written informed consent/assent form used in the study, preferably prior to submission to the IRB.

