#### Adverse Events

Adverse events (AEs) will be coded in MedDRA, version 14.0 or higher. Treatment-Emergent Adverse Event (TEAE) is defined as any AE occurs on or after applying the first dose of study drug. Number and percent of subjects reporting TEAEs will be tabulated by treatment group. Summaries will be presented by body system and preferred term for the ITT population. Similar tables will be presented by severity and relationship to study drug. TEAEs reported by 5% or more subjects for any treatment group will also be summarized. In summaries of incidence rates (frequencies and percentages), severity and relationship to study drug of individual, subjects who report more than one event that are mapped to the same preferred term will be counted only once under the strongest severity and relationship, accordingly. The difference between Test and Reference treatments with regard to the severity and frequency of their dermatological adverse events will be statistically evaluated. Fisher's exact test will be used to compare the proportions of subjects of the two active treatment groups who report any TEAE.

Treatment-Emergent Serious Adverse Events (TESAEs) and TEAEs that led to treatment interruption or discontinuation will be presented in data listings.

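### The SAP's partial-start-date rule can label an adverse event treatment-emergent even when its recorded stop date is before the first dose

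*SAP*

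**What the plan says.** SAP 5.6 (Adverse Events) gives the governing definition: "Treatment-Emergent Adverse Event (TEAE) is defined as any AE occurs on or after applying the first dose of study drug".

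SAP 6.1 says how to apply it when the start date is incomplete. It begins "Handling of partial dates is only considered for the start date". An AE is then treatment-emergent under any one of three branches:

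1. "only the day is missing and the start month/year is the same or after the month/year of the first dose";
2. "the day and month are missing and the start year is the same or greater than the year of the first dose date";
3. "the start date is completely missing".

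No branch mentions the stop date, and the third has no further condition. No other visible text in the SAP or protocol overrides them.

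Three other places matter. Protocol 2.2 has both an approximate onset date and an end date recorded for each AE. Protocol 7.3 states "Adverse event reporting begins from the signing of informed consent/assent", so AEs before the first dose are within the data collected. The concomitant medication part of SAP 6.1 already compares a stop date with the first dose when it classifies medications.

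**The concern.** An AE that ended before the first application cannot have occurred on or after it. If its start date is incomplete, SAP 6.1 can still call it treatment-emergent. Counting an AE as emergent when its timing is unknown is an ordinary cautious convention. In this case the timing relative to dosing is known from the stop date, and the rule does not use it.

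TEAE status feeds the incidence tables, the tables by severity and by relationship, the 5% table, and the Fisher comparison of Test with Reference on subjects with any TEAE (SAP 5.6). An event wrongly admitted appears in those outputs although treatment cannot have caused it. There is also a practical risk: a programmer who sees the conflict between SAP 5.6 and SAP 6.1 would have to settle it without guidance.

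**Working it through.** The plan states no figure on this point, so there is none to reproduce. The check applies the two SAP sections to a set of date patterns.

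**Inputs.** The definition comes from SAP 5.6 and the three branches from SAP 6.1. The dates are illustrative assumptions: first dose 20 March 2013, and a stop date of 18 March 2013 (20 − 18 = 2 days before dosing), 25 March 2013, or missing.

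**Step 1: the rule as written.** Six start-date patterns × three stop-date states = 18 cases. Complete start dates follow SAP 5.6 directly. The stop date does not enter, so each row has one answer.

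| Start date recorded | SAP label, any stop date | Label if stop = 18 March is tested first |
|---|---|---|
| March 2013, day missing | emergent | **not emergent** |
| 2013, day and month missing | emergent | **not emergent** |
| Completely missing | emergent | **not emergent** |
| February 2013, day missing | not emergent | not emergent |
| 15 March 2013 | not emergent | not emergent |
| 2012, day and month missing | not emergent | not emergent |

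**Step 2: add the stop-date condition.** With a stop of 25 March or a missing stop, no label changes. With a stop of 18 March, three labels change, one for each branch. In total 3 of 18 cases change and 18 − 3 = 15 do not. These counts describe the logic; they do not estimate how often such events occur.

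**Step 3: can such an event arise in this trial?** It must begin after consent, end before the first dose and lack a full start date.

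- *For:* Protocol 7.3 starts AE reporting at consent. Protocol 9 requires consent before any withdrawal of current medication done for the research, and refers to a screening phase and to re-screening.
- *Against:* the visible schedule has no separate screening visit. Visit 1 is baseline on Day 1, and the first application is made at the site that day (Protocol 5.11 and 5.16). If consent is also given on Day 1, an AE reported from consent onward cannot have a stop date earlier than the first-dose date.

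A gap is therefore possible, but its length and frequency are not visible.

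**Step 4: effect on the Fisher comparison.** Suppose a fraction *q* of subjects in each arm gains a false TEAE, independently of arm and of true TEAEs. An arm's expected any-TEAE proportion moves from π to π + (1 − π)*q*. The expected difference between Test and Reference becomes

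(π_T − π_R) × (1 − *q*).

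At an assumed *q* = 1% the factor is 1 − 0.01 = 0.99, so the expected difference shrinks by 1% of its own size. The documents give no value for *q*.

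**The case against.** The best defence has four parts.

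- **The opening sentence is ambiguous.** It can be read as saying only that partial stop dates get no rule, with SAP 5.6 still governing whenever the stop date is complete. That is fair for the sentence alone. It does not rescue the branches, which assign a label without regard to any stop date.
- **Inclusion is the cautious error in a safety analysis.** This holds when timing is unknown. It gives no reason to include an event already known to have ended before dosing.
- **Existing controls would catch most cases.** Protocol 11.1 provides for data checks and queries before unblinding, and a pre-dose stop with an incomplete start is an obvious query. This lowers the likely count, but the rule still gives the wrong label to any case that remains.
- **The window may be empty.** With baseline and first application on the same day, there may be no such event. This stands, and it limits the weight of the point.

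A reader might also infer more than the documents support. One inference is that every AE ending before the first dose is counted as treatment-emergent. It is not: an AE with a complete pre-dose start date, or a partial start in an earlier month or year, is correctly left out. Another is that the rule makes the two active arms look alike. The dilution holds only in expectation and is very small. The Fisher test counts subjects, so a false event matters only if it is that subject's sole TEAE. With a handful of events, chance could move the comparison either way.

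**Conclusion.** The point holds in a narrow form. As written, SAP 6.1 contradicts SAP 5.6 for an AE that has both an incomplete start date meeting one of the three branches and a stop date known to precede the first dose. This is a stated rule that gives a wrong label, and not merely a missing detail.

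Its size is small. Affected events are probably few or none, and their number cannot be computed from the documents. The reach is limited to the TEAE tables and the Test-versus-Reference Fisher test; no primary or secondary efficacy analysis depends on it. The conclusion rests on the visible text only. The visit procedures are redacted, so the interval between consent and first dose is unknown. This is a minor correction worth making before unblinding.

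**What to change.** Replace the opening sentence of the AE part of SAP 6.1 with:

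> An AE with a partial or missing start date is not treatment-emergent if its stop date, or the recorded month/year or year of a partial stop date, is before that of the first dose; otherwise the following rules for the start date apply.

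Keep the three branches unchanged. The opening sentence has to be replaced and not merely supplemented. The new condition uses partial stop dates, and it would conflict with a retained statement that only start dates are handled.

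The cost is one SAP sentence and one programming condition. There is a small downside: a wrongly recorded stop date could remove a true TEAE, which is the less safe error. Any AE excluded by this condition should therefore be queried before database lock and shown in the AE listings.
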